7.14 Study Halting Rules

Administration of PLIFUS will be halted if three grade 3 AEs determined to be "probably related" are observed. [name] will inform the DSMB members within 24 hours of this occurrence and will provide the DSMB with AE listing reports. The DSMB will convene an ad hoc meeting by teleconference or in writing as soon as possible. The DSMB will provide recommendations for proceeding with the study. If the study is conducted under an IDE, [name] will inform the FDA of the temporary halt and the disposition of the study.

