5.9 Premature Termination or Suspension of Study

This study may be temporarily suspended or prematurely terminated if there is sufficient reasonable cause. If the study is prematurely terminated or suspended, the PI will promptly inform the IRB and will provide the reason(s) for the termination or suspension.

Circumstances that may warrant termination or suspension include, but are not limited to:

- Determination of unexpected, significant, or unacceptable risk to participants

The study may resume once concerns about safety, protocol compliance, data quality are addressed and satisfy the IRB and DSMB.

6 Study Agent (Study drug, device, biologic, vaccine etc.) and/or Procedural Intervention

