7.11 Classification of an Adverse Event

7.11.1 Severity of Event

For AEs not included in the protocol defined grading system, the following guidelines will be used to describe severity.

- **Mild** – Events require minimal or no treatment and do not interfere with the participant's daily activities.
- **Moderate** – Events result in a low level of inconvenience or concern with the therapeutic measures. Moderate events may cause some interference with functioning.
- **Severe** – Events interrupt a participant's usual daily activity and may require systemic drug therapy or other treatment. Severe events are usually potentially life-threatening or incapacitating.

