7.11.2 Relationship to Study Agent

The research psychiatrist's assessment of an AE's relationship to sonication/sham is part of the documentation process, but it is not a factor in determining what is or is not reported in the study. If there is any doubt as to whether a clinical observation is an AE, the event should be reported. All AEs must have their relationship to study agent assessed. In a clinical trial, the study product must always be suspect. To help assess, the following guidelines are used.

- **Related** – The AE is known to occur with the study agent, there is a reasonable possibility that the study agent caused the AE, or there is a temporal relationship between the study agent and event. Reasonable possibility means that there is evidence to suggest a causal relationship between the study agent and the AE.
- **Not Related** – There is not a reasonable possibility that the administration of the study agent caused the event, there is no temporal relationship between the study agent and event onset, or an alternate etiology has been established.

For all collected AEs, the research psychiatrist who examines and evaluates the participant will determine the AE's causality based on temporal relationship and his/her/their clinical judgment. The degree of certainty about causality will be graded using the categories below.

- **Definitely Related** – There is clear evidence to suggest a causal relationship, and other possible contributing factors can be ruled out. The clinical event, including an abnormal laboratory test result, occurs in a plausible time relationship to drug administration and cannot be explained by concurrent disease or other drugs or chemicals. The response to withdrawal of the drug (dechallenge) should be clinically plausible. The event must be pharmacologically or phenomenologically definitive, with use of a satisfactory rechallenge procedure if necessary.
- **Probably Related** – There is evidence to suggest a causal relationship, and the influence of other factors is unlikely. The clinical event, including an abnormal laboratory test result, occurs within a reasonable time after administration of the drug, is unlikely to be attributed to concurrent disease or other drugs or chemicals, and follows a clinically reasonable response on withdrawal (dechallenge). Rechallenge information is not required to fulfill this definition.

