7.13 Serious Adverse Event Reporting

Any AE considered serious by the PI which meets the definition of an SAE included in Section 8.1.2, Definition of Serious Adverse Event will be submitted on an SAE form to the DCC. The DSMB will receive real-time notification of all SAEs.

We do not believe that this study requires FDA approval (IDE) because the sonication parameters that we are using fall well within the FDA ETC safety guidelines. However, if an IDE is required, we will report any adverse events within 10 calendar days if the information meets the following criteria:

- (A) A single occurrence of an event that is uncommon and known to be strongly associated with drug exposure (e.g., angioedema, hepatic injury, Stevens-Johnson Syndrome);
- (B) One or more occurrences of an event that is not commonly associated with drug exposure, but is otherwise uncommon in the population exposed to the drug (e.g., tendon rupture);
- (C) An aggregate analysis of specific events observed in a clinical trial (such as known consequences of the underlying disease or condition under investigation or other events that commonly occur in the study population independent of drug therapy) that indicates those events occur more frequently in the drug treatment group than in a concurrent or historical control group."

In addition, if the study requires an IDE, we will notify the FDA of any unexpected fatal or life-threatening suspected adverse reaction as soon as possible but in no case later than 7 calendar days of occurrence

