addition to all adverse events recorded by the SAFTEE assessments, the DSMB will receive a report of any additional participant complaints, instances of participant distress, or breaches of confidentiality. Because this is a pilot study with a very small sample size, formal statistical criteria are not identified in advance for a stopping rule. The DSMB may halt the study for reasons of safety—we are not aware of any significant safety concerns. The DSMB must approve the decision to switch from one session of PLIFUS to 3 sessions if no effect is detected after the first 12 completers with good quality imaging data. A failure to detect an effect size of 0.5 or greater compared to sham on the AHRS, DESA, and PSYRATS total score or on GPi functional connectivity after the first 12 participants will define “no effect” and trigger a switch to 3 treatment sessions over 5 days for phase II of the study which will involve an additional 4 participants. The DSMB will also be provided copies of all communications with the IRB. The DSMB will meet prior to initiation of the study and a minimum of every six months and will be provided data regarding enrollment and side effects and a study summary prior to each meeting. [name] and study staff will not attend the closed section of the DSMB meetings. Throughout the study, notification of any Serious Adverse Events (SAEs) as well as any proposed investigator-initiated changes in the protocol will be submitted to the DSMB. Based on its review of the revised protocol, the DSMB will identify the data parameters and format of the information to be regularly reported. All SAEs and adverse events will be tabulated and submitted to the IRB and DSMB in the bi-annual (every 6 months) data reports or at the time of continuing review. AEs will be reported to the IRB annually (at continuing review) if they are expected, related, and harmful. A summary of the outcomes of the safety reviews as prepared for the DSMB along with accumulated adverse events and deviations will be submitted to the IRB as part of an annual progress report at the time of the Continuing Review submission.

8 Clinical Monitoring

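### The only numeric safety halting rule (section 7.14) counts Probably Related events and, as written, leaves out Definitely Related ones

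*Combined protocol and SAP*

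**What the plan says.** - **Section 7.14 (Study Halting Rules).** "Administration of PLIFUS will be halted if three grade 3 AEs determined to be" probably related (the category name is in quotation marks in the protocol) "are observed. [name] will inform the DSMB members within 24 hours of this occurrence". AE listings then go to the DSMB, which meets ad hoc. The sentence has no qualifier such as *at least* or *or higher*.
- **Section 7.11.2 (Relationship to Study Agent).** Certainty about causality is graded in five categories: Definitely, Probably, Possibly, Unlikely and Not Related. The top category is defined by "There is clear evidence to suggest a causal relationship, and other possible contributing factors can be ruled out". Probably Related needs less: other factors need only be unlikely. The text on Possibly Related names the two higher categories as alternative upgrades, so they are distinct labels.
- **Section 7.11.1 (Severity of Event).** "For AEs not included in the protocol defined grading system, the following guidelines will be used to describe severity". Three levels follow: Mild, Moderate and Severe. There are no numbered grades, and the grading system referred to does not appear in the text supplied.
- **Other study-level provisions.** Section 7.13: "The DSMB will receive real-time notification of all SAEs". Section 7.15: "The DSMB may halt the study for reasons of safety". Section 5.9: "This study may be temporarily suspended or prematurely terminated if there is sufficient reasonable cause". Section 7.15 also says that no formal statistical stopping criteria are set in advance, because the sample is very small.

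**The concern.** A halting rule should become easier to meet as the evidence of harm gets stronger. As written, this one does the reverse at the top of the scale: moving a severe event from Probably to Definitely Related takes it out of the count.

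This matters because 7.14 is the only numeric study-level safety trigger in the protocol. The stop for more than 50% worsening on AHRS and DESA (section 2.4.1) ends one participant's procedure. The 0.5 effect-size threshold governs the switch to three sessions and is not a safety rule. The protocol also says that PLIFUS has not been studied before in schizophrenia, the device was built in-house, and exposure may rise to three sessions over 5 days. A mandatory pause should not depend on staff reading past the words of the rule.

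**Working it through.** The protocol states no operating characteristic for the halting rule, so there is no figure to reproduce. The check sets the wording against the protocol's own scales and then against the other safeguards.

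**Step 1: categories covered.** Section 7.11.2 has 5 causality categories. Those at or above Probably Related are Definitely and Probably, so 2. Section 7.14 names 1 of the 2.

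**Step 2: counting.** Let *p* be the number of severe AEs judged Probably Related and *k* the number judged Definitely Related, taking grade 3 to mean Severe. The threshold is 3.

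- Literal count = *p*
- Count if both categories are included = *p* + *k*

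| *p* | *k* | Literal count | Halt? | Count with both | Halt? |
|---|---|---|---|---|---|
| 3 | 0 | 3 | yes | 3 | yes |
| 2 | 1 | 2 | no | 2 + 1 = 3 | yes |
| 2 | any *k* ≥ 1 | 2 | no | 2 + *k* ≥ 3 | yes |
| 0 | 3 | 0 | no | 0 + 3 = 3 | yes |

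The rule counts events, not participants, and the documents give no rate of severe related events. No probability of triggering is therefore offered, and the argument does not need one.

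**Step 3: is the omitted event caught elsewhere?** Take a severe AE, judged Definitely Related, that is not an SAE. Such an event can exist. Under 7.11.1 a Severe event is one that interrupts a participant's "usual daily activity and may require systemic drug therapy or other treatment", and that alone meets none of the SAE criteria in 7.10.2.

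| Provision | Covers this event? | Forces a study-level halt? |
|---|---|---|
| 7.13, real-time DSMB notice | No, SAEs only | No |
| 7.12.1, IRB report within 5 working days, with IRB communications copied to the DSMB (7.15) | Yes, if unexpected and related | No |
| 7.15, DSMB may halt | Yes, once the DSMB knows | No, discretionary |
| 5.9, suspension or termination | Yes | No, discretionary |
| 2.4.1, stop during sonication | Only if symptoms worsen, or distress or suicidal ideation appears, during the procedure | No, one participant |
| 7.10 and 7.15, scheduled safety data to the DSMB (after the first 5 subjects, after 8 completers, otherwise at least every six months) | Yes, at the next review | No |

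Only 7.14 combines a required halt, 24-hour notice and an ad hoc meeting, and its wording leaves this event out.

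**Step 4: the severity term.** Reading grade 3 as Severe, the third of three levels, is the natural inference, but it is not stated. If a five-grade scale were meant, grades 4 and 5 would also fall outside the literal wording.

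**The case against.** The strongest reply is that this is a slip of wording with little practical effect.

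- **Intent.** An event with clear evidence and other causes excluded also satisfies the substance of the Probably Related definition. A DSMB of a statistician and two psychiatrists would hardly treat three definite harms as less than three probable ones. This is very likely right about intent. It does not change what the text says, and 7.11.2 treats the labels as separate.
- **Rarity.** Definitely Related requires other factors to be ruled out, with rechallenge if necessary. Causality is judged by a psychiatrist, and the study psychiatrist is blind to condition (6.1.5). Participants have ongoing psychosis, and the single-session stage gives each of them only one active session. The label should therefore be uncommon. This stands as a limit on how often the gap would matter. It is weaker for the three-session stage, where active treatment is repeated.
- **Overlap with SAEs.** Section 7.11.1 adds that Severe events are usually potentially life-threatening or incapacitating, so many would be SAEs and reach the DSMB at once. This also stands, but *usually* leaves a remainder, and notice is not a halt.
- **IRB route.** The known effects are described as mild and transient, so a severe related event would nearly always be unexpected and reportable within 5 working days. That is slower than 24 hours and requires no pause.
- **Deliberate reliance on the DSMB.** Section 7.15 leaves safety decisions to DSMB judgement because the study is small. That is a reasoned choice, but the protocol also chose to include a fixed trigger, and the trigger should work as intended.

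**Conclusion.** The concern holds. As written, the only numeric study-level halting trigger omits the strongest causality category: it names one of the two that should count, and three severe Definitely Related events score 0 of 3.

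The conclusion rests on the literal wording of 7.14, on 7.11.2 treating the two categories as distinct, and on grade 3 meaning Severe. The practical consequence is limited by the likely intent, the probable rarity of the label under blinding, and the SAE, IRB and DSMB routes. The exposed class is severe, definitely related events that are not SAEs. The change should be made, because the rule gives a wrong result on its own terms, but nothing here suggests the trial is unsafe to run. The undefined grading system is a smaller gap in detail and would not justify a comment by itself.

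**What to change.** Reword the trigger in 7.14 along these lines: *PLIFUS is to be halted once three or more AEs rated Severe (section 7.11.1) and judged Probably or Definitely Related (section 7.11.2) have been observed.* Saying *three or more* and *Severe* also removes the dependence on an undefined grade. In 7.11.1, either define the protocol grading system or delete the reference to it.

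The cost is one sentence in 7.14 and one phrase in 7.11.1, submitted as a protocol amendment. Sample size, visits and analysis are unaffected.

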7.15 Safety Oversight

It is the responsibility of [name] to oversee the safety of the study. This safety monitoring will include careful assessment and appropriate reporting of adverse events as noted above. Medical monitoring will include a regular assessment of the number and type of serious adverse events. [name] will remain blinded to treatment condition (sonication versus sham) but the DSMB will have access to unblinded safety and efficacy data. Because this is a small pilot study, decisions regarding safety and efficacy, which may include increasing the frequency of treatment from one session to three sessions for 4 additional participants if a single session of PLIFUS does not produce measurable effects in the first 12 completers with good quality imaging data, or discontinuing the study due to adverse events, will be made by the DSMB without statistical tests since the sample size will be quite small (n=12).

Our existing data safety and monitoring board (DSMB) will monitor this study. [name] will be responsible for convening the DSMB, for providing information about enrollment, retention, efficacy, and side effects, and will be responsible for reporting minutes from the DSMB to the IRB. The DSMB has monitored five clinical studies over the past 9 years and is comprised of a statistician and two psychiatrists with extensive experience conducting clinical trials in patients with schizophrenia and in participating on DSMBs. If specific risks emerge additional members with expertise in the area of the potential safety issue will be added to the DSMB. The DSMB will approve the protocol prior to initiation of the study. The DSMB will review site performance, including recruitment, subject retention, protocol violations, and data quality reports. The DSMB will receive an unblinded report of all safety data (adverse events as defined above, including change scores on the AHRS and DESA, the SAFTEE assessments or findings upon clinician assessment) after completion of the first 5 subjects in addition to reports for bi-annual meetings. In

addition to all adverse events recorded by the SAFTEE assessments, the DSMB will receive a report of any additional participant complaints, instances of participant distress, or breaches of confidentiality. Because this is a pilot study with a very small sample size, formal statistical criteria are not identified in advance for a stopping rule. The DSMB may halt the study for reasons of safety—we are not aware of any significant safety concerns. The DSMB must approve the decision to switch from one session of PLIFUS to 3 sessions if no effect is detected after the first 12 completers with good quality imaging data. A failure to detect an effect size of 0.5 or greater compared to sham on the AHRS, DESA, and PSYRATS total score or on GPi functional connectivity after the first 12 participants will define “no effect” and trigger a switch to 3 treatment sessions over 5 days for phase II of the study which will involve an additional 4 participants. The DSMB will also be provided copies of all communications with the IRB. The DSMB will meet prior to initiation of the study and a minimum of every six months and will be provided data regarding enrollment and side effects and a study summary prior to each meeting. [name] and study staff will not attend the closed section of the DSMB meetings. Throughout the study, notification of any Serious Adverse Events (SAEs) as well as any proposed investigator-initiated changes in the protocol will be submitted to the DSMB. Based on its review of the revised protocol, the DSMB will identify the data parameters and format of the information to be regularly reported. All SAEs and adverse events will be tabulated and submitted to the IRB and DSMB in the bi-annual (every 6 months) data reports or at the time of continuing review. AEs will be reported to the IRB annually (at continuing review) if they are expected, related, and harmful. A summary of the outcomes of the safety reviews as prepared for the DSMB along with accumulated adverse events and deviations will be submitted to the IRB as part of an annual progress report at the time of the Continuing Review submission.

8 Clinical Monitoring

A study psychiatrist will be present during all sessions of PLIFUS and sham. Participants will be monitored during and after sonication until psychiatrically cleared by the study psychiatrist 1 hour after completion of each session. Participants will be contacted 24-48 hours and 7 days after each treatment period and symptoms, side effects and suicidality assessed.

9 Statistical Considerations

This is a pilot study intended to obtain preliminary data to guide future studies. The analysis will primarily be descriptive for this purpose and, due to the small sample size, effect sizes will be the primary signal of target engagement. Consistent with other studies in the field, we have selected an effect size of 0.5 as our threshold. In addition, there is a pre-planned review of results after completion of the first 5 participants; the administration of PLIFUS/sham will be increased from one session to three sessions over 5 days if an effect size of 0.5 or greater with PLIFUS is not detected in change from baseline in GPi functional connectivity or symptom response compared to sham.

The primary statistical analysis will be performed in completers without imputation of missing data and will be change in primary outcomes (GPi functional connectivity and symptom severity) from baseline to the first measure post-sonication or sham (immediately post-sonication for symptoms; 10-30 minutes for fMRI). PLIFUS and sham PLIFUS will be compared using a linear mixed effects model with baseline measures (GPI functional connectivity and severity of psychotic symptoms) as continuous variables; treatment (PLIFUS or sham) and sequence as categorical variables; and participant as a random effect. Similar secondary exploratory analyses will be performed at additional time points (symptom severity during sonication, 60 minutes, 1 day and 7 days after sonication). Secondary analyses of other outcome measures (BPRS total score, PSYRATS and CGI) will be analyzed following the same approach. Safety measures, including the SAFTEE and C-SSRS will be summarized descriptively. If the study design is adapted (sonication increased to 3 sessions) after the first 12 completers with good quality imaging data, results from the first 12 completers and subsequent 4 participants will be analyzed separately.

Sample Size

This is an unfunded pilot trial intended to assess feasibility and to collect preliminary data on safety and target engagement to support future grant proposals. Given these goals and fiscal constraints, we selected a total of 12 completers as an appropriate sample size to provide pilot data with reasonable reliability.

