We will use the ultrasound pulse parameters used by Cain et al ³⁹ for sonication of the globus pallidus (see previous paragraph) because their experiment demonstrated hemodynamic effects without adverse effects in healthy subjects and the stimulation parameters were very low-intensity and extremely low risk. If we do not see effects on functional connectivity or symptoms after the first 5 participants and if the single sessions are well-tolerated, we will switch to repeated dosing, applying three PLIFUS or sham sonifications over 5 days since repeated exposures may be required to produce detectable effects. A single session of PLIUS will include 5 minutes net total dosage of PLIFUS. The exposure uses ten 30 sec blocks of PLIFUS sonication with 30 sec rests in-between spread over ten minutes. Sonication will be delivered (Fig. 3) in low-amplitude pulses using a carrier wave frequency: 361 kHz, pulse repetition frequency: 100 Hz, and duty cycle: 5 % yielding an I_{spta} 1.5 W/cm² at the Gpi. The acoustic intensity used is in the range of FDA and Electrotechnical Technical Commission (ETC) regulation standards for diagnostic and therapeutic ultrasound, respectively ²⁸.

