7.9 Assessment of Safety

7.10 Specification of Safety Parameters

Safety will be assessed by close monitoring by a study psychiatrist during and for 1 hour after each sonication/sham session by assessment of psychiatric symptoms and side effects (SAFTEE & addendum). SAFTEE, SAFTEE addendum, and CSSRS will be repeated one day and one week after each session. The difference between post-sonication and post-sham safety measures will be assessed for safety. In addition to serious adverse events that will be reported immediately, these data will be provided to the DSMB after the first 8 completers. If the dose is increased to 3 sessions, safety data will be provided to the DSMB after the 4 completers at the higher dose.

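### Section 9 (first paragraph) and Section 2.1.4 decide the move from one to three sessions after 5 participants; every other numbered statement of the rule says 12

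*Combined protocol and SAP*

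**What the plan says.** The trial has one dose-decision rule: if a single session shows no effect of at least 0.5 against sham, dosing moves to three sessions over 5 days. The document gives two different points for that decision.

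**After 5 participants**
- Section 9, first paragraph: "there is a pre-planned review of results after completion of the first 5 participants". The rest of the sentence requires the increase to three sessions if 0.5 is not reached on GPi connectivity or symptom response.
- Section 2.1.4: "If we do not see effects on functional connectivity or symptoms after the first 5 participants", and provided single sessions are well tolerated, the trial switches to repeated dosing.

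**After 12**
- Section 9, second paragraph: "If the study design is adapted (sonication increased to 3 sessions) after the first 12 completers with good quality imaging data", then "results from the first 12 completers and subsequent 4 participants will be analyzed separately".
- Section 7.15: the DSMB must approve the "switch from one session of PLIFUS to 3 sessions if no effect is detected after the first 12 completers with good quality imaging data". Earlier in the section its remit covers the increase "if a single session of PLIFUS does not produce measurable effects in the first 12 completers with good quality imaging data".
- The Protocol Summary (Brief Summary, Objectives, Population, Number of participants, Statistical Analysis) and Sections 3, 4.1, 5.7, 6.1.7, 6.1.8 and 13.8 also use 12.

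Section 3.2 states the rule without a number. Separately, Section 7.15 schedules an unblinded safety report to the DSMB "after completion of the first 5 subjects in addition to reports for bi-annual meetings".

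**The concern.** Consecutive paragraphs of the statistics section give incompatible triggers for the same action, and nothing in the document says which takes precedence. The 5-participant sentence is an instruction, not background, and it sits where an analyst or DSMB member would look first.

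Two things are at stake: the dose that later participants receive, and whether the planned single-session dataset is ever completed. The Sample Size text in Section 9 chose 12 completers so that the pilot data would be reasonably reliable. A switch at 5 would abandon that number. The 5-participant text also does not say how many participants would follow on three sessions; the 12-completer rule says 4.

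**Working it through.** The plan has no calculation to reproduce: Section 9 gives no alpha, power or SD, and justifies 12 completers on feasibility and cost. The main check is therefore textual.

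**1. Count the statements.** Two places say 5 (Section 2.1.4; Section 9, first paragraph). Those saying 12 are: Protocol Summary 5, Section 3 one, 4.1 one, 5.7 one, 6.1.7 one, 6.1.8 one, 7.15 three, Section 9 second paragraph one, 13.8 one. That is 5+1+1+1+1+1+3+1+1 = 15. The unit varies slightly: Sections 6.1.7 and 6.1.8 say only completers, one sentence in 7.15 says only participants, and the rest attach the imaging-quality condition.

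**2. Can both hold as two planned looks?** If the rule triggered at 5, there would never be 12 single-session completers, so the split into the first 12 and the next 4 would be empty. No 12-completer statement mentions an earlier efficacy look.

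**3. Is the 5 simply the DSMB safety report?** That report covers adverse events, AHRS and DESA change scores, SAFTEE and clinician findings. It does not list GPi connectivity, which is one of the two outcomes the Section 9 review would judge. The Section 9 sentence is tied to the 0.5 threshold and the dose change.

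**4. Shortfall.** 12 − 5 = 7 if all of the first 5 are completers with good-quality imaging. Section 9 does not require that of the 5, so each unusable scan adds one. Hence at least 7.

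**5. Illustration, one outcome.** Assumption (the protocol defines no standardiser): effect size d = mean within-person PLIFUS-minus-sham difference ÷ SD of the differences, normal data. With no true effect, P(d ≥ 0.5) = P(t with n−1 df ≥ 0.5√n).
- n=5: P(t₄ ≥ 1.118) = 0.163
- n=12: P(t₁₁ ≥ 1.732) = 0.056

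Using the noncentral t with noncentrality d√n, the probabilities at n=5 and n=12 are 0.526 and 0.515 for a true effect of 0.5, and 0.755 and 0.844 for 0.8. The 95% CI half-width, t₀.₉₇₅/√n, is 1.24 SD at n=5 and 0.64 SD at n=12.

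**6. Illustration, two outcomes.** Assumptions: connectivity and one symptom score, correlation 0, 0.5 or 0.8; switch only if both are below 0.5; first 5 nested in the 12; 400,000 simulated trials per setting. Ranges are over the three correlations.

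| True effect | Switch at 5 | Switch at 12 | Switch at 5 but not at 12 |
|---|---|---|---|
| 0 on both | 70.1–77.1% | 89.2–91.6% | 2.5–3.2% |
| 0.5 on both | 22.5–36.6% | 23.5–37.8% | 10.9–12.6% |
| 0.8 on both | 6.0–16.0% | 2.4–9.2% | 5.0–10.8% |
| 0.8 on one, 0 on the other | 20.4–24.4% | 14.7–15.6% | 12.3–14.5% |

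The last column is the one that bears on this point: about 3–15% of trials would leave the single-session stage at 5 when the 12-completer rule would not have switched.

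**The case against.** The strongest reply is that nobody would act on the 5. Every operative section uses 12: design, participant numbers, dose escalation, dose modification, DSMB decision, separate analysis and payments. Section 2.1.4 is background. Section 7.15 requires DSMB approval and defines the absence of an effect at 12. Harm would need someone to follow one sentence against the paragraph after it and against the DSMB's own definition. This stands, and it lowers the severity. It does not remove the contradiction, because the sentence is current and mandatory.

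The illustrations are also open to challenge. Section 7.15 names three symptom scales as well as connectivity, and how they combine is unclear. With no true effect and independent outcomes, the chance that at least one reaches 0.5 is 0.300 at n=5 and 0.108 at n=12 with two outcomes, but 0.509 and 0.204 with four. So the figures show direction and rough size and do not describe the actual rule. At a true effect of 0.5 the overall switch rates at 5 and 12 are nearly equal.

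A reader might infer that a review at 5 inflates a type I error, or that the 16% is a rate of false positive findings. The documents do not support that. All results are declared exploratory, and under the Section 9 text reaching 0.5 at 5 changes nothing: the trial continues on one session.

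**Conclusion.** The contradiction is real and needs no calculation: two sentences say 5, and fifteen statements say 12. The 12-completer rule governs by weight of text, and the 5 is probably left over, though the document does not say so. If the 5 were applied and triggered, at least 7 of the 12 planned single-session completers with good-quality imaging would be lost, and the planned analysis of the first 12 and the next 4 could not be carried out.

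Severity is moderate. The probabilities (16% against 6% for one null outcome; about 3–15% of trials switching at 5 but not at 12 under the two-outcome rule) rest on an assumed paired effect size, normal data and an assumed decision rule.

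A reader might go further and conclude that the trial is set to escalate on five participants. The document does not support that: DSMB approval of the switch is written only for 12.

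**What to change.** In Section 9, first paragraph, and in Section 2.1.4, replace the 5-participant trigger with the first 12 completers with good-quality imaging data, or delete the 5-participant switch text. Keep the 5-subject DSMB report in Section 7.15 and describe it as safety only.

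The cost is a protocol wording amendment and notice to the DSMB, with no added participants, visits or procedures.

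Three neighbouring matters are separate points and are not needed for this correction: the effect-size standardiser, how connectivity and the symptom scales combine in the rule, and the difference between the 5-subject safety report and Section 7.10, where "these data will be provided to the DSMB after the first 8 completers".
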